6.0 ANALYSIS POPULATIONS

6.1 Modified Intent-to-Treat Population

The Intent-to-Treat (ITT) population will include all randomized patients. All efficacy analyses will be conducted on the modified ITT (mITT) population, which is defined as all randomized patients who complete the surgical procedure. In analyses based on the mITT population, subjects will be analyzed according to their randomized treatment assignment. Analyses based on the mITT population will be considered the primary analyses of efficacy.

6.2 Per Protocol Population

The Per Protocol (PP) population will include all randomized patients who have no major protocol violations. Major protocol violations will be identified based on blinded data after the study is completed, but before database lock and the unblinding of the treatment group assignments. All efficacy analyses will be repeated on this population. In analyses based on the PP population, subjects will be analyzed according to their randomized treatment assignment. Analyses based on the PP population will be considered secondary analyses of efficacy.

6.3 Safety Population

The Safety population will include all study patients who undergo surgery (implant or sham). All safety analyses will utilize this population. In analyses based on the Safety population, subjects will be analyzed according to the actual treatment received.

7.0 EFFICACY ANALYSES

The primary analyses of the primary efficacy endpoint will be comparisons of the least-squares mean (LSM) change from baseline in the Fugl-Meyer Motor Scale score at Week 24 of SB623 treated subjects (pooling all SB623 doses) to sham surgery control subjects for the genotyping subgroup variables defined in Section 5.6. For each genotyping subgroup variable, the relationship between the subgroup variable and the primary efficacy endpoint will be examined in the following manner. An analysis of covariance (ANCOVA) will be performed with terms for treatment (pooled SB623 or sham surgery), subgroup, the treatment-by-subgroup interaction, and the baseline Fugl-Meyer Motor Scale score. Within each subgroup category, the LSM and its standard error will be presented for the two treatments, together with a 95% confidence interval for the LSM. The difference in LSMs between treatments and the corresponding 95% confidence interval will also be presented, as well as the p-value for the test of the null hypothesis that the LSMs are equal for the two treatments. In order to examine whether the treatment effect differs for different categories of the subgroup variable, an F-test will be used to test the null hypothesis that the coefficient of the interaction term equals 0. Missing observations will not be imputed.

In addition, the primary efficacy endpoint, the change from baseline in the FMMS score at Week 24 among all patients, will be analyzed to examine dose response for the genotyping subgroup variables defined in Section 5.6. As for the primary analysis, an analysis of covariance will be performed. The model will include terms for SB623 dose, subgroup, the SB623 dose-by-subgroup interaction, and the baseline Fugl-Meyer Motor Scale score. Dose will be treated as a continuous variable, and the control treatment will not be included in this analysis. The p-value for the test of the null hypothesis that the coefficient of SB623 dose equals 0 will be presented. In order to examine whether the dose effect differs for different values of the subgroup variable, an F-test will be used to test the null hypothesis that the coefficient of the interaction term equals 0 and the p-value will be presented.

Descriptive statistics for the FMMS score at Week 24 and the corresponding change from baseline will be presented by treatment group (control, pooled SB623, and each SB623 dose) and subgroup category for each genotyping subgroup variable. Tables and graphs will be presented summarizing the mean change from baseline in the FMMS score over time by treatment group (pooled SB623 and control) and subgroup category for each genotyping subgroup variable, and tables will be presented by SB623 dose group and subgroup category for each genotyping subgroup variable. The tables will present descriptive statistics. The graphs will plot the mean changes (\pm standard error) over time. The graphs will also present the p-value at each post-baseline timepoint from a two-sample t-test testing the null hypothesis that the true mean change is equal for the two treatments.

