3.4 Determination of Sample Size

For a two-sample t-test to show superiority of SB623 over sham surgery control, assuming 80% power, alpha of 0.05, a two-tailed test, and 3:1 randomization, a sample size of 48 (36 subjects in the treatment group and 12 subjects in the control group) is required. This assumes that the mean change from baseline to Week 24 in the FM-Motor Scale score is 10.0 for the treatment group (pooling all SB623 doses) and 3.0 for the control group, with an assumed standard deviation of 7.25 in each group. Based on an 8% upward adjustment to compensate for dropout patients, a total of approximately 52 subjects will be required. Since the analysis of efficacy is to be based on the modified ITT population, subjects will continue to be enrolled in the study until there are a total of approximately 52 subjects in the mITT population. The vast majority of subjects will be from outside of Japan; however, a sufficient number of Japanese patients are to be enrolled in order to address Japanese regulatory requirements.

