The primary efficacy endpoint will also be analyzed using an analysis of covariance model with the following terms: treatment, the presence of prior (i.e., at baseline) antibodies to donor cell HLA antigens, the interaction between treatment and the presence of prior antibodies to donor cell HLA antigens, the baseline FMMS score, and the GOS-E score at screening to test the null hypothesis that the coefficient of the interaction term equals 0.

The relationship between anti-HLA antibodies and the primary efficacy endpoint will be examined. Descriptive statistics for the primary efficacy endpoint will be presented by treatment group and whether or not the subject experienced an increase of antibodies to donor HLA antigens from baseline to Week 24. A normal approximation test will be used to test the null hypothesis that the differences in means between the pooled SB623 group and the control group are equal for subjects with an increase of antibodies to donor HLA antigens from baseline to Week 24 and those without an increase. Analogous analyses will be performed for whether or not a subject experienced the formation of antibodies post treatment to Week 24 (for subjects with no antibodies at baseline).

The primary efficacy endpoint will be summarized using descriptive statistics for the following subgroups of interest:

- Age at Informed Consent (18-<50 years of age, 50-75 years of age)
- Gender
- GOS-E score at screening (3, 4, 5, or 6)
- Baseline FMMS score (0-50, 51-100)
- Lot (SB623 doses only)
- Percentage cell viability (\leq sample median value, $>$ sample median value)

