3.2 Method of Assigning Subjects to Treatment

Two groups, Group 1 and Group 2, will receive SB623 and sham surgery, respectively, in a 3:1 randomization scheme. Group 1 will be further randomized in a 1:1:1 ratio to receive either 2.5 million, 5 million, or 10 million SB623 cells. Randomization will be performed via an interactive web/voice response system (IXRS). For subjects enrolled outside of Japan, the randomization will be stratified by Glasgow Outcome Scale-Extended (GOS-E) score (i.e., scores 3, 4, 5 or 6); for subjects in Japan, the randomization will not be stratified.

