3.4 Changes to the Protocol-Specified Analyses

No changes were made to the protocol-specified analyses.

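### The genotype and antibody ANCOVAs of Week 24 FMMS change leave out GOS-E, which stratifies randomisation outside Japan and is in every other specified covariate-adjusted FMMS model

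*SAP*

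**What the plan says.** SAP Appendix C (genotyping) and Appendix D (antibody) each specify the same model for the Week 24 change in FMMS, in Section 7.0: "An analysis of covariance (ANCOVA) will be performed with terms for treatment (pooled SB623 or sham surgery), subgroup, the treatment-by-subgroup interaction", plus baseline FMMS. Section 5.2 of each appendix confirms that baseline FMMS is the only adjustment. The dose-response model in each Section 7.0 replaces treatment with dose, excludes the control group and again adjusts only for baseline FMMS.

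On allocation, Section 3.2 of both appendices says that outside Japan "the randomization will be stratified by Glasgow Outcome Scale-Extended (GOS-E) score"; in Japan it is not stratified. Section 8.1 of the protocol agrees. No other stratification factor is named.

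The main SAP (Appendix A, Section 10.1) also has an ANCOVA of the primary endpoint on antibodies. Its terms include "the interaction between treatment and the presence of prior antibodies to donor cell HLA antigens", baseline FMMS and GOS-E at screening.

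Section 3.4 of Appendices C and D reports: "No changes were made to the protocol-specified analyses". Neither appendix says why GOS-E was left out.

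**The concern.** When randomisation is stratified on a factor, the usual practice is to carry that factor into the analysis. Otherwise any variation it explains stays in the error term although the design has already balanced it between arms. The main SAP follows this practice and the two supplements do not.

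Two things are at stake. The first is precision, in a trial with about 13 controls that are then split by genotype or antibody status. The second is consistency: subgroup estimates in Appendices C and D are adjusted differently from the primary result beside which they will be read. This is sharpest for antibodies, where two treatment-by-antibody tests with different covariates are planned, and both appear in the integrated table list (Tables 14.2.4.9 and 14.2.24.1).

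**Working it through.** **1. The plan's own sample size.** Inputs from main SAP Section 3.4: "assuming 80% power, alpha of 0.05, a two-tailed test, and 3:1 randomization"; an SD of 7.25 in both arms; and a mean change that "is 10.0 for the treatment group (pooling all SB623 doses) and 3.0 for the control group".

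Controls = (1 + 1/3) × [7.25 × (1.960 + 0.842) / 7]² = 11.23, rounded up to 12. With three times as many treated, this reproduces "a sample size of 48 (36 subjects in the treatment group and 12 subjects in the control group) is required". Noncentral-t power at 36 and 12 is 80.9%. Then 48 × 1.08 = 51.84, so about 52 patients, or 39 and 13. These figures are the base for step 3.

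**2. The FMMS models side by side.**

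| Place in SAP | Model | GOS-E? |
|---|---|---|
| Main, 5.2 and 10.1 | Primary and dose-response MMRM | Yes, with visit interaction |
| Main, 5.2 and 10.3 | FMMS in patients with both deficits, UE-FM, LE-FM (MMRM) | Yes, with visit interaction |
| Main, 5.2 and 10.3 | FMMS, UE-FM and LE-FM responder logistic models | Yes |
| Main, 5.2 and 10.1 | ANCOVA on baseline donor-HLA antibodies | Yes |
| Appendix B, 7.1 | Japan supplement MMRMs | Yes, with visit interaction |
| Appendix E, 7.1 | Head MRI subgroup MMRMs | Yes, with visit interaction |
| Appendix C, 5.2 and 7.0 | Genotype ANCOVA, treatment and dose | **No** |
| Appendix D, 5.2 and 7.0 | Antibody ANCOVA, treatment and dose | **No** |

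Appendices D and E carry the same date (8 October 2018) and handle GOS-E differently for the same endpoint.

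**3. Size of the loss.** Let R² be the share of the residual variance, after baseline FMMS, that GOS-E explains. The documents give no value, so a range is assumed.

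- Inflation of the standard error from omission = 1/√(1 − R²) − 1.
- Precision lost, in patients = 52 × R².
- Standard error of the overall difference without GOS-E = 7.25 × √(1/13 + 1/39) = 2.32; with GOS-E, multiply by √(1 − R²).

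| Assumed R² | SE inflation | Patients' worth lost, of 52 | SE with GOS-E | Power with GOS-E (difference 7) |
|---|---|---|---|---|
| 0 | 0% | 0 | 2.32 | 84.0% |
| 0.05 | 2.6% | 2.6, about 3 | 2.26 | 85.8% |
| 0.10 | 5.4% | 5.2, about 5 | 2.20 | 87.6% |
| 0.20 | 11.8% | 10.4, about 10 | 2.08 | 91.1% |

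Without GOS-E, power is 84.0% in every row. The standard errors and powers describe the overall comparison of 52 patients. The subgroup contrasts start from larger standard errors.

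**4. Effect on the test.** The treatment-by-subgroup ANCOVA was simulated 4,000 times per setting: 52 patients, all stratified by GOS-E in blocks of four, and a subgroup of about 30%. The test is of the treatment effect averaged over subgroups.

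| Assumed R² | Type I error without / with GOS-E | Power without / with GOS-E |
|---|---|---|
| 0 | 5.4% / 5.4% | 80.2% / 80.0% |
| 0.10 | 3.5% / 4.6% | 80.6% / 83.5% |
| 0.30 | 2.2% / 5.2% | 81.4% / 90.0% |

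Simulation error near 5% is about √(0.05 × 0.95/4000) = 0.3 percentage points. In roughly 1% of runs (0.7¹³ ≈ 0.01) no control falls in the smaller subgroup and the interaction cannot be estimated. A re-run without those cases gave the same pattern. It also showed that the interaction test stays close to its nominal level with or without GOS-E, because GOS-E is not balanced by design inside subgroups. For that test the loss is precision only.

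**5. Cost in degrees of freedom.** With a two-category subgroup the ANCOVA has 5 parameters, so 52 − 5 = 47 residual degrees of freedom, or 46 with GOS-E. With three HLA categories it is 52 − 7 = 45, or 44 with GOS-E.

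**The case against.** The strongest reply is that these are exploratory analyses without multiplicity control and that a short covariate list suits sparse subgroups. The omission can cost precision and make a test conservative, but it does not create false positives. If GOS-E does not predict FMMS change beyond baseline FMMS, it costs nothing. All of that stands, and it keeps the point minor. It does not explain why the main SAP's antibody ANCOVA, with similar subgroups, can afford the covariate.

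Some stronger readings are tempting but not supported.

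- *Every FMMS analysis except these uses GOS-E.* This is true only of the specified covariate-adjusted models. The t-tests on the graphs, the normal-approximation antibody test, the Kolmogorov-Smirnov test and the correlations are unadjusted. Models behind the post-hoc tables are not described.
- *The plan will give two conflicting answers to one antibody question.* Main SAP Section 10.1 gives no threshold for prior antibodies. Appendix D Section 5.6 defines pre-existing antibodies as MFI above 1000 or a positive virtual T or B cell result. The two variables are closely related, but nothing shows that they classify patients identically, and two p-values need not conflict.
- *The supplements breach the protocol while declaring no changes.* Protocol Sections 18.2.2.3 and 18.2.2.4 leave exploratory and subgroup detail to the SAP. This is an inconsistency within the SAP.
- *The ANCOVA is inferior because it drops patients without a Week 24 value.* The main SAP's antibody model is also a single-visit ANCOVA and loses the same patients.
- *At R² of 0.20 the loss is 13 of 52 patients.* Thirteen is the number of extra patients needed to compensate, 52/0.80 − 52. The precision lost is 52 × 0.20 = 10.4.

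One further objection stands. The SAP addendum records that post-hoc analyses were added after the interim results were unblinded, so changing a specified covariate set now could itself be post hoc. The fix allows for this.

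**Conclusion.** The point holds as a minor one. The treatment and dose-response ANCOVAs in Appendices C and D omit GOS-E without explanation. In this they differ from every other specified covariate-adjusted FMMS model, including the main SAP's antibody ANCOVA.

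The size rests on an assumed R². Over 5% to 20%, the standard error is 2.6% to 11.8% larger than it need be; at zero there is no loss. The conservatism in step 4 applies to the overall treatment contrast and assumes that every patient was stratified. Japanese patients are not, so the real effect would be somewhat smaller, although the SAP expects most patients to come from outside Japan. For within-subgroup contrasts the main consequences are lost precision and chance GOS-E imbalance left unadjusted.

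**What to change.** Add GOS-E at screening as a continuous covariate, as in main SAP Section 5.2, to the treatment and dose-response ANCOVAs in Section 7.0 of Appendices C and D, and amend Section 5.2 of each to match. The variable is already collected and costs one degree of freedom.

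If these analyses have already been run on unblinded data, keep the specified ANCOVA and report the GOS-E-adjusted version beside it as a labelled sensitivity analysis.

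For antibodies, use one definition of baseline donor-specific antibody and one covariate set in main SAP Section 10.1 and Appendix D, and name one treatment-by-antibody interaction test as principal. This costs a few lines of text and no new data.

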8.0 SAFETY ANALYSES

The summary of SAEs will be limited to treatment emergent SAEs, which are defined as any serious adverse event with onset on or after the initiation of treatment or any adverse event already present that worsens in intensity following exposure to study treatment.

For each treatment group (control patients, pooled SB623 patients, and each SB623 dose group) and each category of each genotyping subgroup variable, the following results will be presented: number and percentage of subjects with at least one SAE and descriptive statistics for the number of SAEs per patient. For each category of each genotyping subgroup variable, a two-sided Fisher's Exact Test will be used to test for a difference between treatments (pooled SB623 versus control) in the proportion of patients with at least one SAE. For each treatment group, a two-sided Fisher's Exact Test will be used to test for a difference among categories of the subgroup variables in the proportion of patients with at least one SAE.

For each genotyping subgroup variable, a logistic regression analysis of SAE incidence will be performed. The model will include terms for the genotyping subgroup variable, treatment (pooled SB623 or control), and the genotyping subgroup variable by treatment interaction. The p-value for each term in the model will be presented. A statistically significant interaction term would indicate that the effect of treatment on SAE occurrence is different among the categories of the genotyping subgroup variable.

For each genotyping subgroup variable, a dose response analysis of the incidence of SAEs will be performed using a logistic regression model with terms for the genotyping subgroup variable, SB623 dose (as a continuous variable), and the genotyping subgroup variable by SB623 dose interaction. The control group will be excluded from these analyses. The p-value for each term in the model will be presented. A statistically significant interaction term would indicate that the effect of dose on SAE occurrence is different among the categories of the genotyping subgroup variable.

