7.0 EFFICACY ANALYSES

The primary analyses of the primary efficacy endpoint will be comparisons of the least-squares mean (LSM) change from baseline in the Fugl-Meyer Motor Scale score at Week 24 of SB623 treated subjects (pooling all SB623 doses) to sham surgery control subjects for the antibody subgroup variables defined in Section 5.6. For each antibody subgroup variable, the relationship between the subgroup variable and the primary efficacy endpoint will be examined in the following manner. An analysis of covariance (ANCOVA) will be performed with terms for treatment (pooled SB623 or sham surgery), subgroup, the treatment-by-subgroup interaction, and the baseline Fugl-Meyer Motor Scale score. Within each subgroup category, the LSM and its standard error will be presented for the two treatments, together with a 95% confidence interval for the LSM. The difference in LSMs between treatments and the corresponding 95% confidence interval will also be presented, as well as the p-value for the test of the null hypothesis that the LSMs are equal for the two treatments. In order to examine whether the treatment effect differs for different categories of the subgroup variable, an F-test will be used to test the null hypothesis that the coefficient of the interaction term equals 0. Missing observations will not be imputed.

In addition, the primary efficacy endpoint, the change from baseline in the FMMS score at Week 24 among all patients, will be analyzed to examine dose response for the antibody subgroup variables defined in Section 5.6. As for the primary analysis, an analysis of covariance will be performed. The model will include terms for SB623 dose, subgroup, the SB623 dose-by-subgroup interaction, and the baseline Fugl-Meyer Motor Scale score. Dose will be treated as a continuous variable, and the control treatment will not be included in this analysis. The p-value for the test of the null hypothesis that the coefficient of SB623 dose equals 0 will be presented. In order to examine whether the dose effect differs for different values of the subgroup variable, an F-test will be used to test the null hypothesis that the coefficient of the interaction term equals 0 and the p-value will be presented.

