9.0 SAFETY ANALYSES

The summary of AEs will be limited to treatment emergent SAEs, which are defined as any serious adverse event with onset on or after the initiation of treatment or any serious adverse event already present that worsens in intensity following exposure to study treatment.

For each treatment group (control patients, pooled SB623 patients, and each SB623 dose group) and each category of each antibody subgroup variable, the following results will be presented: number and percentage of subjects with at least one SAE and descriptive statistics for the number of SAEs per patient. For each category of each antibody subgroup variable, a two-sided Fisher's Exact Test will be used to test for a difference between treatments (pooled SB623 versus control) in the proportion of patients with at least one SAE. For each treatment group, a two-sided Fisher's Exact Test will also be used to test for a difference between categories of the subgroup variables in the proportion of patients with at least one SAE.

For each antibody subgroup variable, a logistic regression analysis of SAE incidence will be performed. The model will include terms for the antibody subgroup variable, treatment (pooled SB623 or control), and the antibody subgroup variable by treatment interaction. The p-value for each term in the model will be presented. A statistically significant interaction term would indicate that the effect of treatment on SAE occurrence is different between the two categories of the antibody subgroup variable.

For each antibody subgroup variable, a dose response analysis of the incidence of SAEs will be performed using a logistic regression model with terms for the antibody subgroup variable, SB623 dose (as a continuous variable), and the antibody subgroup variable by SB623 dose interaction. The control group will be excluded from these analyses. The p-value for each term in the model will be presented. A statistically significant interaction term would indicate that the effect of dose on SAE occurrence is different between the two categories of the antibody subgroup variable.

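### The genotype and antibody dose-response ANCOVAs promise a p-value for the dose coefficient alongside a dose-by-subgroup interaction, without saying which slope that coefficient is

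*SAP*

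**What the plan says.** SAP Appendix C 7.0 (genotype) and Appendix D 7.0 (antibody) use the same dose-response ANCOVA for the Week 24 change in FMMS: "The model will include terms for SB623 dose, subgroup, the SB623 dose-by-subgroup interaction, and the baseline Fugl-Meyer Motor Scale score". Only SB623 patients enter: "Dose will be treated as a continuous variable, and the control treatment will not be included in this analysis".

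Two tests follow. The first is on dose: "The p-value for the test of the null hypothesis that the coefficient of SB623 dose equals 0 will be presented". The second is an F-test of whether "the coefficient of the interaction term equals 0 and the p-value will be presented".

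Descriptive output is planned as well. In Appendix C, "tables will be presented by SB623 dose group and subgroup category for each genotyping subgroup variable", and Appendix D has the parallel sentence.

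Neither appendix names the coding of subgroup, a SAS procedure, a type of sums of squares or a contrast. For the pooled-treatment comparison, the same sections are more complete: "Within each subgroup category, the LSM and its standard error will be presented for the two treatments", with the difference, its confidence interval and its p-value.

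The SAE logistic dose models have the same structure. Appendix C 8.0 includes "SB623 dose (as a continuous variable), and the genotyping subgroup variable by SB623 dose interaction" and Appendix D 9.0 includes "SB623 dose (as a continuous variable), and the antibody subgroup variable by SB623 dose interaction". Both present a p-value for every model term.

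**The concern.** Once dose and subgroup interact there is no single dose effect in the model; there is one slope per category. The coefficient labelled dose is whichever combination of those slopes the parameterisation produces, so the sentence does not define a test until the coding is fixed. Two programmers following this text could correctly produce different p-values from the same data.

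A reader of the dose-response tables will take that p-value as the dose effect. The integrated SAP table list keeps such tables for BDNF and APOE (14.2.22.3 and 14.2.22.4) and for the combined antibody variable (14.2.24.4). If the reference category happens to be the small one, the test rests on few patients and will usually look null even when dose matters.

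**Working it through.** **The plan's own figures.** The SAP gives no power or precision for these tests. The inputs that bear on them come from main SAP 3.4: SD 7.25 and about 52 subjects randomised 3:1. That calculation reproduces: 12 sham plus 36 SB623 is 48, with 80.9% power by exact t for a difference of 7.0, and 48 × 1.08 = 51.8, or about 52. So SB623 has about 52 × 3/4 = 39 patients, or 13 at each of 2.5, 5 and 10 million cells.

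**What the coefficient is.** Take two categories A and B and the model

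E(change) = b0 + b1·dose + b2·G + b3·dose·G + b4·baseline.

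- G = 0 for A, 1 for B: b1 is the slope in A.
- G = 0 for B, 1 for A: b1 is the slope in B.
- G = −1 or +1 (sum-to-zero): b1 is (slope A + slope B)/2, whatever the category sizes. The Type III test coincided with this one in the example below.

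The test of b3 is the same in all three.

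**One simulated data set** (36 SB623 patients; 27 in A, 9 in B):

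| Parameterisation | Dose coefficient | Dose p | Interaction p |
|---|---|---|---|
| A as reference | 0.264 | 0.48 | 0.555 |
| B as reference | 0.751 | 0.30 | 0.555 |
| Sum-to-zero | 0.507 | 0.21 | 0.555 |

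The third coefficient is the mean of the first two: (0.264 + 0.751)/2 = 0.5075, equal up to rounding. The dose p-value moves with the coding and the interaction p-value does not.

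**Approximate precision.** Assumptions not in the documents: a 25% minority category, a common slope of 0.8 FMMS points per million cells, and categories balanced over dose.

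Mean dose is 17.5/3 = 5.83. The squared deviations are 11.11 + 0.69 + 17.36 = 29.17, and × 13 = 379.2.

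- No interaction: SE = 7.25/√379.2 = 0.37.
- Majority slope: 7.25/√(0.75 × 379.2) = 0.43.
- Minority slope: 7.25/√(0.25 × 379.2) = 0.74.
- Equal-weighted average: ½√(0.43² + 0.74²) = 0.43.

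The ratios 0.8/SE are about 2.15, 1.86, 1.07 and 1.86. By noncentral t these give power of about 55%, 44%, 18% and 44%.

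**Simulation.** Same assumptions, but category membership falls at random over doses, so precision is a little worse. Mean SEs are about 0.38 without the interaction, 0.44 for the majority slope and 0.83 for the minority slope.

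| Dose test | Common slope 0.8: rejects | No dose effect: rejects |
|---|---|---|
| Majority as reference | about 43% | about 5% |
| Minority as reference | about 16% | about 5% |
| Sum-to-zero | about 39% | about 5% |
| Model without interaction | about 51% | about 5% |

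Under the common slope, the two reference codings disagree on significance in about 44% of trials. Repeat runs move these figures by a point or two.

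**Other assumptions.** With 12 patients per dose, 30% in the smaller category and a common slope of 1, the reference codings reject in 55% and 24% and disagree in 53%. With slopes of 0 in the larger and 2 in the smaller category, they reject in 5% and 70%. Those two are correct answers to different questions, so here the harm is that the table would not say which question was answered.

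**The case against.** The strongest reply is that this is a small gap in an exploratory analysis whose real question is answered elsewhere. The interaction F-test does not depend on coding and directly asks whether the dose effect differs by subgroup. Main SAP 10.1 already tests dose response in all SB623 patients, with no subgroup term. The analyses carry no multiplicity control, and the primary comparison is untouched. All of that stands and limits the weight of the point. It does not give the printed dose p-value a meaning.

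Some stronger readings do not hold:

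- *The dose p-value is all that is reported.* No: the interaction p-value and the descriptive dose-by-subgroup tables are planned too. None of these is an estimated slope with an interval.
- *The test is of the reference category's slope.* Only under reference coding. The SAP fixes no coding, and a sum-to-zero test does not depend on a reference level.
- *The choice of coding inflates false positives.* Taken singly, each version rejects in about 5% of trials with no dose effect.
- *Slopes and intervals are absent from the planned output.* This can be said only of the narrative text. Table shells are listed as appendices to both plans but are not in the text available here.
- *The SAE models share the same numerical problem.* Their wording is a p-value per term, which could mean a Type III test, and the text directs interpretation to the interaction. The figures above are for the linear model and do not carry over to the logistic ones.

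**Conclusion.** The point holds as one of specification. In both appendices the dose p-value has no defined meaning until a parameterisation or contrast is stated, and the text plans no dose slope or interval within subgroup, although the treatment comparison in the same sections gets that treatment. The analyst would be left with a choice that changes the power of the dose test from about 43% to about 16% in the illustration and flips significance in about 44% of trials. Those figures rest on an assumed 25% minority category and an assumed common slope of 0.8; only the SD and the approximate group size come from the SAP. The consequence is ambiguity and lost power in exploratory tables. It is worth correcting because those tables are retained for the report and the correction is easy. The SAE dose models deserve the same clarification, but no size is claimed for them.

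**What to change.** In SAP Appendix C 7.0 and Appendix D 7.0, replace the sentence on the dose coefficient with:

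> The estimated dose slope, its 95% confidence interval and p-value will be presented within each subgroup category, estimated from the interaction model, together with the interaction F-test.

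For an overall dose effect, refer to the main SAP 10.1 analysis, or use the ANCOVA without the interaction and say so.

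In the SAE logistic dose models (Appendix C 8.0, Appendix D 9.0), report the log-odds slope per unit of dose with its confidence interval within each category where it can be estimated. Otherwise, name the contrast behind the dose p-value.

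The cost is a wording change and a few ESTIMATE statements, plus a check that the table shells have room for the results. No new data are needed.
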